#### Loss of Confidentiality

Any time information is collected; there is a potential risk for loss of confidentiality. Every effort will be made to keep the participant's information confidential; however, this cannot be guaranteed.

### **10. Subject Safety and Data Monitoring:**

#### Adverse Events and Reporting

For the purposes of collecting and evaluating all information found during this clinical study, an adverse event (AE) is any undesirable or unexpected experience that occurs after informed consent has been obtained without regard to the possibility of a causal relationship and without regard to treatment group assignment. A serious adverse event (SAE) is any adverse event occurring that: results in death, is life threatening, results in inpatient hospitalization or prolongation of existing hospitalization, results in a persistent or significant disability/incapacity, or results in congenital anomaly/birth defect. UT Southwestern requires AEs/SAEs to be reported if they are unexpected, definitely study-related, and put the participant and the participant pool at an increased risk of harm. The non-reportable AEs/SAEs will be tracked and summarized on the continuing review.

Each participant will be seen or spoken to on a weekly basis and assessed for the presence of any adverse reactions. AEs and SAEs will be monitored using standard definitions. A participant with AEs or SAEs will be followed until they return to baseline or stabilize regardless of whether the participant has discontinued or completed the study. AEs and SAEs will be reported to the Data Safety Monitoring Board, comprised of clinicians with a keen awareness of the risks for acutely ill psychiatric patients and the general disease course for those hospitalized with mania or bipolar disorder. Details can be found in the separate DSMB Charter.

#### Worsening of Illness

Given that re-hospitalization is the primary outcome of this study, it is expected that some proportion of participants will again require admission for stabilization of their psychiatric symptoms. Research study staff will continuously monitor the status of psychiatric symptoms and ensure that participant safety is of upmost concern. Each participant will be instructed and expected to continue

treatment with his/her mental health providers and to remain on his/her prescribed psychotropic medications throughout the study. Psychiatric treatments that the participant receives will be noted and included in the analyses. We note that the participant's usual psychiatric treatment will be uncontrolled in this study; to standardize such treatment would not be practical or ethically feasible given the individualized nature of treatment regimens and responses. If a participant reports psychiatric symptoms that raise concerns about safety such as imminent, potentially dangerous behavior, research staff will consult with the study PI and/or study physician and may contact the participant's current treatment providers, as permission to contact these providers will be obtained as early in the study as is available. Research staff will encourage participants to seek immediate help in these cases. Additionally, research staff may arrange for emergency assessment if a participant presents as a danger to self or others, in consultation with the study PI and/or the study physician. If the participant is deemed an acute risk for serious consequences, including suicide, the physician will direct the measures necessary to get the participant to safety, using clinic specific crisis management procedures which may include getting the participant to the Psychiatric Emergency Room. The staff at the Psychiatric ER would then determine the necessary steps and would decide if the participant's symptoms warrant admission to the hospital.

### **11. Procedures to Maintain Confidentiality:**

Blood specimens for UT Southwestern patients will be provided to Quest Diagnostics for analysis, and identifying information (e.g., name) that could be linked to the patient's identity will be removed prior to sending for analysis. The blood provided to Quest will have the participant's year of birth to allow for accurate analysis and correctly link the results to the participant. The results of this test will be de-identified and added to the rest of the de-identified data. Once de-identified, only the identified investigators can learn/discover the names of participant. All samples which are sent to [name] lab at Johns Hopkins for analysis of the biological factors will also be de-identified. Similar to the blood specimen data, the results will be combined with the wider data set in which the participants identifying information is not present.

Blood specimens for JPS patients will be assessed within JPS's central laboratory and reported per usual clinical procedure in the JPS electronic medical record. No identifying information for patients will travel outside the JPS system for these laboratory analyses.

previous study on which this study is based was able to find variables which correlated significantly with risk of re-hospitalization with a sample size of n=66, indicating that this sample size is adequate for the detection of an effect of the probiotic therapy. Secondary and exploratory outcomes, such as the number of new illness episodes, symptom severity, changes in cognitive test scores, or the effect of treatment on the levels of inflammatory markers over the course of the study will be performed by means of chi-square, analysis of variance, and other analyses comparing the placebo- and probiotic-supplemented groups.

1. McIntyre RS. Long-term treatment of bipolar disorder in adults. *The Journal of clinical psychiatry*. 2011;72(2):e06. Epub 2011/03/09. doi: 10.4088/JCP.9089tx1cc. PubMed PMID: 21382301.

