**Protocol**

**Title: A Probiotic Intervention to Prevent Relapse Following Hospitalization for Mania**

**1. Introduction and Purpose:**

A probiotic containing the microorganisms Lactobacillus GG and Bifidobacteria lactis strain Bb12 has recently been evaluated in a population hospitalized for acute mania. Findings from this trial indicated that those taking the adjunctive probiotic had a reduced rate of relapse, as defined by hospital readmission, compared to those taking adjunctive placebo. We will conduct a replication trial to confirm the clinical findings and extend understanding of the mechanism by which the probiotic affects these clinical outcomes.

Primary Aim 1. To determine if adjunctive probiotic administration can reduce relapse for participants first hospitalized for mania. *Hypothesis:* Participants receiving adjunctive probiotic microorganisms vs. adjunctive placebo will have a lower rate of relapse as defined by a re-hospitalization (e.g., admission to an inpatient unit) during the 24 week study period.

Secondary Outcomes. The number of new mood episodes, the severity of psychiatric symptoms, and changes in cognitive scores over the 24 week study period will be evaluated.

Exploratory Aim 1. To study the effect of probiotic therapy in lowering the levels of inflammatory markers following an acute episode of mania. *Hypothesis:* Participants receiving adjunctive probiotic microorganisms vs. adjunctive placebo will have reduced levels of antibodies to casein, gliadin, and the NMDA receptor, and reduced levels of C-Reactive protein and the cytokine TNF alpha following 24 weeks of probiotic therapy.

Exploratory Aim 2. To evaluate changes in the gut microbiota following probiotic administration.

*Hypothesis:* Probiotic administration will enrich the gut microbiota of participants with the given microorganisms and these changes may correlate to changes in the peripheral inflammatory markers being measured.

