### **3. Concise Summary of Project:**

We will conduct a 24-week, randomized, double-blind, placebo-controlled trial of adjunctive probiotic therapy in 66 persons hospitalized with a manic or mixed episode. The study will take place at UT Southwestern Medical Center, Dallas, TX and John Peter Smith (JPS) Health Network, Fort Worth, TX. The active study compound will consist of capsules containing approximately  $10^9$  colony forming units of the probiotic organisms, Lactobacillus GG and Bifidobacteria lactis strain Bb12. The dose has been selected because it has been used safely in other probiotic trials, was well-tolerated by the participants in two previous trials of individuals with schizophrenia or mania, and was utilized in the original trial on which this replication is based. This dose is higher than that available in most commercially-sold health food supplements. Following hospital discharge, participants will be randomized to receive adjunctive probiotic or placebo for a 24 week period. It is anticipated that of the 66 participants randomized, ~50 (75%) will complete the full 24 weeks of the study. The primary outcome is relapse, defined as re-hospitalization (e.g., admission to an inpatient unit) for psychiatric symptoms following a previous hospital discharge by at least 2 weeks. The occurrence of new mood episodes, the severity of psychiatric symptoms, and any changes in cognitive test scores over the course of the study will also be evaluated. Changes in the levels of inflammatory markers as well as changes in gut microbiota will be evaluated at three time intervals over the course of the study.

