### Randomization

Double-blind randomization will occur after eligibility has been established at the baseline visit. Each participant will be randomly assigned to receive either the probiotics compound or placebo, which they will begin to receive at the week 0 in-person visit. Block randomization based on number of previous hospitalizations in the last year will be used to assign participants to the two treatment groups. Only the statistician and the study staff which prepare the medications will be aware of participant assignment; the principal investigators and other research staff will remain blinded until all participants have completed the study.

The double-blind treatment phase will last from randomization at Week 0 until the end of 24 weeks. After randomization, the participant will be seen in-person again at weeks 4, 8, 12, 16, 20, and 24 when symptom evaluations and assessments of dietary intake will be performed. Phone contact will be made with the participant every week between in-person study visits to promote adherence to the study and to identify any study-related problems.

Week 0: Once the participant is deemed eligible to participate in the study, they will be randomized and receive study compound. The coordinator will ask about any changes to medications, current treatment or any re-hospitalizations. They will also complete the ISS to evaluate mood.

Phone contacts: The weekly phone contacts (~20mins, Weeks 1-3, 5-7, 9-11, 13-15, 17-19, 21-23) will collect reports of any adverse events, including current pregnancy, medication compliance by participant self-report, report on current treatment and any re-hospitalizations, updates to the medication list, and assessment to determine the current diagnosis and add any new mood episodes. Participants will be asked to complete the ISS via a link sent to their email via REDCap.

Virtual visits, Weeks 4, 8, 16, and 20 (~1hr): These in-person visits will collect reports of any adverse events, including pregnancy, updates on current treatment and medications and notation of any re-hospitalizations, pill counts and/or participant report of compliance, assessment to ascertain the

current diagnosis and any new mood episode, the YMRS, MADRS, BPRS, QLESQ, CSSRS, ISS. Weight and vitals will also be collected, and a brief evaluation with a psychiatrist will be conducted.

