**In-person visits, Weeks 12 and 24 (~2hrs):** These in-person visits will collect reports of any adverse events, including pregnancy, updates on current treatment and medications and notation of any re-hospitalizations, pill counts and/or participant report of compliance, assessment to ascertain the current diagnosis and any new mood episode, YMRS, MADRS, BPRS, QLESQ, the Sheehan Disability Scale, CSSRS, ISS, TMT, COWAT, Stroop task, and RAVLT, and assessment of dietary intake of participant based on a 24 hour recall of food intake. During the recall, each participant will be shown a selection of portion sizes to obtain the most accurate information. The participant will also be questioned about his/her intake of any foods or supplements containing probiotics. Blood, throat swabs, stool and urine samples, as well as weight and vitals will also be collected. A brief evaluation with a psychiatrist will be conducted. At week 24 (or, in case of early discontinuation, the last study visit done by participant), an exit survey will be administered to evaluate participant's perception of in-person vs. virtual study visits.

**Follow-up Phone Call, 6 months following completion of study compound (~15 min):** This call will collect information about any (re)hospitalization for either psychiatric or medical reasons, any current treatment, and complete the ISS and the short-form CSSRS.

	Baseline	Week 0	Weeks 1-3	Week 4	Weeks 5-7	Week 8	Weeks 9-11	Week 12	Weeks 13-15	Week 16	Weeks 17-19	Week 20	Weeks 21-23	Week 24
SCID	X													
Physical Exam & Psych Eval	X													
Blood draw, stool collection, urine collection	X							X						X
Height (BL only), Weight, and Vitals, Clinician Follow-up	X			X		X		X		X		X		X
Tx &/or Hospitalization, ISS	X	X	X	X	X	X	X	X	X	X	X	X	X	X
Dispense Study Compound		X		X		X		X		X		X		
New Mood Episode		X	X	X	X	X	X	X	X	X	X	X	X	X
BPRS, YMRS, MADRS, QLESQ, CSSRS	X			X		X		X		X		X		X
TMT, COWAT, RAVLT, Stroop	X							X						X
TII	X													
Sheehan Disability Scale	X							X						X
Dietary Questionnaire	X							X						X
Exit survey														X

The participants will receive:

- \$40 for completion of the Baseline Visit.

- \$40 for Week 0.
- \$180 for phone visits (18 visits, \$10 each).
- \$180 for in-person visits (6 visits, \$30 each).
- \$100 for additional lab work and assessments at Weeks 12 and 24 (2 visits, \$50 each):
- \$50 for a completion bonus provided at the completion of the Week 24 visit.

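### Section 13 commits to no baseline-adjusted analysis, and no use of the randomization factor, for the secondary and inflammatory-marker outcomes

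*Combined protocol and SAP*

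**What the plan says.** One sentence in Section 13 covers new mood episodes, symptom severity, cognitive change and inflammatory markers. Their analysis "will be performed by means of chi-square, analysis of variance, and other analyses comparing the placebo- and probiotic-supplemented groups". No method is tied to any one outcome.

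Other sections bear on how that sentence can be read:

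- **Secondary outcomes (Section 1):** "The number of new mood episodes, the severity of psychiatric symptoms, and changes in cognitive scores over the 24 week study period will be evaluated". Cognition is framed as change, symptoms as severity and episodes as a count.
- **Markers:** Exploratory Aim 1 predicts lower levels "following 24 weeks of probiotic therapy". Section 3 speaks of changes in markers that "will be evaluated at three time intervals over the course of the study".
- **Schedule table (Section 4):** the row "BPRS, YMRS, MADRS, QLESQ, CSSRS" is marked at baseline and at Weeks 4, 8, 12, 16, 20 and 24. The row "TMT, COWAT, RAVLT, Stroop" and the blood draw are marked at baseline and at Weeks 12 and 24. New mood episodes are recorded at every contact from Week 0.
- **Randomization (Section 4):** "Block randomization based on number of previous hospitalizations in the last year will be used to assign participants to the two treatment groups". The categories are not given.
- **Completion (Section 3):** of 66 randomized, about "50 (75%) will complete the full 24 weeks of the study".
- **Discontinuation:** people who stop early are asked to do the final visit. The plan does not say which scheduled visit that assessment represents.

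The covariates that Section 13 does name (gender, age and diagnosis), its censoring rule and its requirement of one visit after randomization are all written for the time-to-rehospitalization analysis.

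**The concern.** A baseline value is scheduled for every score and marker, and the blocking factor is known for every participant. Nothing in Section 13 commits the analysis to adjusting for either. For symptom severity, ANOVA of final scores, of change scores or of repeated measures all fit the text, and none of these uses baseline as a covariate. For cognition, and on the wording of Section 3 probably for markers, baseline enters by subtraction. That is less precise than adjustment, and less precise than ignoring baseline when the correlation is below 0.5.

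With 66 participants and about 50 completers, that precision matters. An open choice among analyses that can give different answers also weakens whatever is reported.

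A second, smaller issue is the episode count. About a quarter of participants are expected not to complete, and no allowance is made for weeks observed. If follow-up differs by arm, raw counts favor the arm observed for less time.

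**Working it through.** **Plan's own figure.** 66 × 0.75 = 49.5, which agrees with about 50 completers. The plan gives no SD, correlation, episode rate, significance level or power for these outcomes, so there is no precision figure to reproduce.

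**Assumptions.** 1:1 allocation, 25 completers per arm, 80% power, two-sided 5%, and correlation r between baseline and Week 24 of 0.3, 0.5 or 0.7.

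**Week-24 comparison.** With outcome variance 1, the variance factors are:

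- final score: 1
- change score: 2(1 − r) = 1.4, 1.0, 0.6
- baseline-adjusted: 1 − r² = 0.91, 0.75, 0.51

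The final-score detectable difference from the noncentral t (48 df) is 0.809 SD. The other entries scale with the square root of the factor, for example 0.809 × √1.4 = 0.957. The adjusted analysis uses 47 df.

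| Analysis | r = 0.3 | r = 0.5 | r = 0.7 |
|---|---|---|---|
| Final-score ANOVA | 0.81 | 0.81 | 0.81 |
| Change-score ANOVA | 0.96 | 0.81 | 0.63 |
| Baseline-adjusted | 0.77 | 0.70 | 0.58 |

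To match 25 per arm with adjustment, final scores need 25/(1 − r²) = 27.5, 33.3 or 49.0 per arm. Change scores need 50/(1 + r) = 38.5, 33.3 or 29.4. With 33 and 17 completers instead of 25 and 25, all figures rise by about 5.5% and the order is unchanged.

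**Mixed model against adjusted completers.** This was simulated with 4,000 runs per setting, 33 per arm and 16 of 66 leaving uniformly over 24 weeks. An unstructured-covariance model lowered variance by a further 2% to 10% with six visits and 0% to 7% with two. Most of the gain is therefore baseline adjustment.

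**Week 24 or the average over visits.** With equal correlations, the baseline-adjusted mean of the six post-baseline visits has variance (1 + 5r)/6 − r² = 0.327, 0.333, 0.260.

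- Effect immediate and constant: the detectable difference is 0.46, 0.47, 0.41 SD.
- Effect growing linearly to Week 24: the average effect is 3.5/6 = 0.583 of the final one, so the Week-24 difference needed is 0.79, 0.80, 0.71 SD, against 0.77, 0.70, 0.58 SD for the Week-24 contrast.

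Neither target is more precise in both cases.

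**Randomization factor.** Suppose it explains 5% or 10% of outcome variance. Ignoring it makes the nominal 5% test 2·P(Z > 1.96/√0.95) = 4.4% or 2·P(Z > 1.96/√0.90) = 3.9%. Including it multiplies the detectable difference by about 0.975 or 0.949. The gain is larger only if the factor is strongly prognostic. With a two-level factor worth 1 SD, 33 per arm and a 0.6 SD effect, simulated power of the adjusted analysis rose from 0.59, 0.68, 0.82 to 0.70, 0.78, 0.91.

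**Episode counts.** If dropout p is uniform over 24 weeks, mean observed time is 1 − p/2 of full follow-up.

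- Equal dropout: no bias.
- Assumed 35%/15% split: null ratio 0.925/0.825 = 1.12, or 0.89 the other way.
- Assumed 30%/20% split: 0.90/0.85 = 1.06, or 0.94.
- Chance of a 20-point gap when true dropout is 25% in both arms: z = 0.20/√(2 × 0.25 × 0.75/33) = 1.88, p = 0.06.

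At a true rate ratio of 0.50 and one placebo episode per 24 weeks, simulated power with equal dropout was 35% for ANOVA of raw counts and 37% for a robust rate model. Against chi-square on any episode, an overdispersed rate model gained about 6 to 12 points at one episode per 24 weeks and nothing at 0.5. Under the null with 10% against 40% dropout, chi-square rejected in 7% to 12% of runs and the rate model in 3% to 5%.

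**The case against.** The strongest reply is that Section 13 leaves room for other analyses, so neither a covariate-adjusted nor a mixed model is excluded. That is right. A reader might infer that the plan rules out the better method or prescribes a wrong one, and the text supports neither. What stands is that nothing is committed, and the only methods named do not adjust for baseline.

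A reader might also infer that baseline is ignored throughout. It is not: cognition is to be analyzed as change, and Section 3 uses the same word for markers. For those outcomes the comparison is change score against adjustment, which at r = 0.7 is only 0.63 against 0.58 SD.

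A third tempting reading is that chi-square or ANOVA will give biased results for mood episodes. The plan assigns neither test to that outcome, and nothing in it suggests that dropout will differ by arm. With equal dropout there is no bias, and a rate model adds little or no power unless episodes are frequent.

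Finally, Week 24 should not be imposed on symptoms and cognition. The plan refers to the whole study period, which fits an average or a trajectory at least as well.

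It is also fair to say that these outcomes are secondary or exploratory and that every magnitude rests on assumed correlations, rates and dropout splits.

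**Conclusion.** The concern holds as a gap in commitment, with a concrete and inexpensive improvement available. Under the assumptions above, baseline adjustment gives a smaller detectable Week-24 difference than either final or change scores at each correlation tried. The margin ranges from about 5% (against final scores at r = 0.3) to about 29% (against final scores at r = 0.7: 0.578 against 0.809 SD). Against change scores it ranges from about 19% at r = 0.3 to about 8% at r = 0.7. At r = 0.5, adjustment on 25 per arm is worth about 33 per arm without it.

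The randomization factor adds little unless it is strongly prognostic. The case for including it is mainly that the analysis should reflect the design. The rate model for mood episodes is protection against unequal follow-up, not a gain in power, and ranks lower. The primary time-to-rehospitalization analysis is not affected, and the microbiota analyses are not part of this point.

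**What to change.** **Main change.** For the symptom scales, quality-of-life scales, cognitive scores and inflammatory markers (log scale where skewed), replace ANOVA with a mixed model on all scheduled post-baseline visits. It should contain treatment by visit, baseline value by visit, and the randomization factor in the categories used for blocking. Use an unstructured covariance. With six visits that means 21 parameters and may not converge at 66 participants, so name one simpler fallback in advance; heterogeneous first-order autoregressive is a candidate. With two visits it means 3 parameters.

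**Target.** Name the Week-24 contrast for markers, in line with Exploratory Aim 1. For symptoms and cognition, have the sponsor choose Week 24 or the average over visits before unblinding, according to how the effect is expected to develop.

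**Early exits.** State that an early final assessment is not counted as Week 24, and say how it will be used.

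**Optional, lower priority.** Analyze the number of new mood episodes with a rate model that has log weeks observed as offset and standard errors robust to overdispersion. The offset does not fully correct for dropout related to illness.

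**Cost.** Analysis-plan wording and modest programming. No new data, visits or participants are needed.
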